11.2.5 Definition of Suspected Adverse Reaction

Suspected adverse reaction (SAR) means any AE for which there is a reasonable possibility that the trial treatment caused the AE. *Reasonable possibility* means there is evidence to suggest a causal relationship between the trial treatment and AE. An SAR implies a lesser degree of certainty about causality than AR, which means an AE caused by a trial treatment.

11.2.6 Definition of Unexpected Adverse Event or Unexpected Suspected Adverse Reactions

An AE or SAR is considered *unexpected* if it is not listed in the Investigator's Brochure or is not listed at the specificity or severity that has been previously observed.

11.3 Serious Adverse Events

11.3.1 Definition of Serious Adverse Events

An AE is considered an SAE if it meets any of the following criteria:

- Results in death;
- Is life-threatening;

Note: An AE or SAR is considered *life-threatening* if, in the view of either the investigator or sponsor, its occurrence places the patient at immediate risk of death. It does not include an AE or SAR that, had it occurred in a more severe form, might have caused death;

- Requires inpatient hospitalization or prolongs existing hospitalization;
- Results in persistent or significant disability or incapacity;

That is, the event severely or permanently disrupts the patient's ability to perform normal life functions or daily activities.

- Results in a congenital anomaly or birth defect;
- Is medically significant (Important Medical Event);

Medical and scientific judgment should be exercised in deciding whether SAE reporting is appropriate in other situations, such as important medical events that may not be immediately life-threatening or result in death or hospitalization but may jeopardize the patient. Examples of such events are allergic bronchospasm requiring treatment in an emergency room, serious blood dyscrasias, or seizures/convulsions that do not result in hospitalization. The development of drug dependence or drug abuse would also be examples of important medical events.

11.3.2 Serious Adverse Event Reporting Requirements

Any SAE that occurs from the time the consent is signed through 90 days following cessation of trial treatment or EOS (whichever is later), or 28 days following cessation of trial treatment if the patient initiates new anti-cancer therapy, whether or not the SAE is related to the trial treatment (SD-101 and/or pembrolizumab), **must be reported to Dynavax or its designee within 24 hours of investigator awareness of the event.** The contact information for reporting SAEs is provided in the Study Reference Manual. General SAE reporting instructions are as follows:

- Submit SAE documents according to instructions in the Study Reference Manual.
- Record all SAEs on the AE CRF.
- For SAEs, record the primary event on the AE CRF; describe events occurring secondary to that primary event on the SAE form in the narrative description of the case.
- Death is an outcome, not an event. Record the event that resulted in the death as the fatal event on the AE CRF.
- For hospitalizations for surgical or diagnostic procedures, record the illness leading to the surgical or diagnostic procedure as the SAE, not the procedure itself. Capture the procedure in the narrative as part of the action taken in response to the illness.
- Elective hospitalizations will not be considered SAEs and do not need to be reported. Complications that prolong elective hospitalizations should be recorded as SAEs. Emergency room visits of less than 24 hours do not meet the criterion of hospitalization for SAE reporting purposes.

The SAE report should contain, at a minimum, the following information:

- Patient identifiers (ie, patient number)
- Suspected medicinal product
- AE term (must be listed as serious)
- Contact information for person reporting event

The relationship of the SAE to trial treatment will be assessed by the investigator (Section 11.4.2). Follow-up information should be actively sought and submitted as it becomes available.

The investigator will assess relationship to trial treatment. In addition, the sponsor will assess relationship to trial treatment and determine expectedness to SD-101 based on the current SD-101 Investigator's Brochure and to pembrolizumab based on the pembrolizumab Investigator's Brochure. The sponsor will report all SD-101 suspected and unexpected serious

adverse reactions (SUSARs) to regulatory authorities as expedited reports in accordance with applicable regulatory requirements (eg, 21 CFR 312.32[c] in the US). All other SAEs will be reported as part of regulatory safety updates, as required, such as in annual reports. Merck will be responsible for pembrolizumab global reporting requirements.

11.4 Adverse Event Severity and Relationship to Trial Treatment

11.4.1 Severity Grading of Adverse Events

The severity of predefined AEs and other health changes will be assessed and confirmed by the investigator and will be graded using the NCI CTCAE Version 4.03 grading scale by system organ class ([National Cancer Institute 2010](#)). If the appropriate grading or description cannot be applied, then the investigator may elect to use the adapted NCI CTCAE, Version 4.03 ([Table 11-1](#)) to assess the AE.

Table 11-1: National Cancer Institute Common Terminology Criteria for Adverse Events (CTCAE, Version 4.03)

AE Severity	Definition
Grade 1	Mild; asymptomatic or mild symptoms; clinical or diagnostic observations only; intervention not indicated
Grade 2	Moderate; minimal, local or noninvasive intervention indicated; limiting age-appropriate instrumental ADL ^a
Grade 3	Severe or medically significant but not immediately life-threatening; hospitalization or prolongation of hospitalization indicated; disabling; limiting self-care ADL ^b
Grade 4	Life-threatening consequences; urgent intervention indicated
Grade 5	Death related to AE

Source: Adapted from NCI CTCAE, Version 4.03 ([National Cancer Institute 2010](#))

ADL = Activities of Daily Living; AE = adverse event; CTCAE = common terminology criteria for adverse events; NCI = National Cancer Institute.

^a Instrumental ADL refer to preparing meals, shopping for groceries or clothes, using the telephone, managing money, etc.

^b Self-care ADL refer to bathing, dressing and undressing, feeding self, using the toilet, taking medications, and not bedridden.

NOTE: For all AEs and SAEs, if there is a change in the severity after onset of either an AE or SAE, the AE or SAE should be reported as a single entry with the maximum severity grading captured.

11.4.2 Relationship of Adverse Events to Trial Treatment

The investigator will determine the relationship of the AE to trial treatment using the definitions provided in Table 11-2.

Table 11-2: Definitions for Relationship of Adverse Events to Trial Treatment

Relationship to Trial Treatment	Definition
Not Related	Another cause of the event is most plausible; or clinically plausible temporal sequence is inconsistent with the onset of the event and the trial treatment administration; or a causal relationship is considered biologically implausible.
Possibly Related	An event that follows a reasonable temporal sequence from administration of the trial treatment or a known or expected response pattern to the suspected drug, but that could readily have been produced by a number of other factors.
Probably Related	An event that follows a reasonable temporal sequence from administration of the trial treatment, and there is a biologically plausible mechanism for trial treatment causing or contributing to the AE, and the event could not be reasonably explained by the known characteristics of the patient's clinical state. In addition, the relationship may be confirmed by improvement on stopping the trial treatment and reappearance of the event on repeated exposure.

AE = adverse event.

The investigator will follow all related AEs observed during the trial until the AEs are considered resolved or until trial termination.

The investigator will follow all SAEs, whether assessed as possibly, or probably related, or not related to study treatment, until the SAEs are considered stable, resolved, or until EOS, or the patient begins new anti-cancer therapy (whichever is earlier).

The sponsor may request additional follow-up on specific unresolved AEs.

11.5 Reporting and Documentation of Pregnancy

Any patient who becomes pregnant during the trial will be discontinued from all trial treatments and followed for pregnancy outcome. Any pregnancy in a partner of a male trial participant must be reported to Dynavax or its designee. Follow-up information should be actively sought by the investigator and submitted to Dynavax or designee as soon as it becomes available. The investigator will complete the pregnancy reporting form and all other relevant CRFs.

Uncomplicated pregnancies are not considered an AE/SAE. A complicated pregnancy or a pregnancy with an adverse outcome may meet criteria for an AE or SAE and would then also be reported according to the appropriate requirements.

A patient who becomes pregnant will be instructed to report the pregnancy to the trial site as soon as possible. A report of the pregnancy will be completed by the investigator or designee and will document details of the pregnancy, outcome of pregnancy, and details of delivery. The patient should be followed by the investigator through the remainder of the pregnancy for safety assessments.

Pregnancies and breastfeedings that occur from Day 1 through 120 days after the last dose of trial treatment or 28 days following cessation of trial treatment if the patient initiates new anti-cancer therapy (whichever is earlier) must be reported by the investigator. The sponsor or designee must be notified as soon as possible once the trial site learns of a pregnancy or breastfeeding. Pregnancy report forms provided by the sponsor or designee must be completed and submitted to Dynavax or designee. The contact information for reporting pregnancy is provided in the Study Reference Manual.

12.0 STATISTICAL METHODS

NOTE: As of Amendment 9, Phase 1 of the trial is complete. All analyses related to data collected in Phase 1 will be performed as detailed in this section. As of Amendment 9, the trial will stop collecting efficacy and exploratory data, and the collection of safety data has been simplified. Thus, after trial completion, only selected analyses related to data collected in Phase 2 of the trial will be performed, and exploratory objectives will not be pursued.

This section outlines the statistical analysis strategy and procedures for the trial. If, after the trial has begun, changes are made to primary or exploratory objectives and/or hypotheses, or to the statistical methods related to those objectives and/or hypotheses, then those changes, along with an explanation as to when and why they occurred, will be listed in the Clinical Study Report (CSR) for the trial. Post hoc exploratory analyses will be clearly identified in the CSR. No imputations will be made for missing data. Additional details of the statistical analyses to be performed will be provided in the trial Statistical Analysis Plan.

12.1 General

This trial is designed to allow preliminary assessments of safety, biological activity, and biomarkers. No pre-specified hypothesis testing will be performed. All analyses of demographics, safety, biological activity, and biomarkers will be descriptive.

Injection-site reactions, AEs, SAEs, and abnormal laboratory values will be summarized by the proportion of patients who experience them.

ORR will be presented as the proportion of patients who achieved CR or PR. The DCR will be presented as the proportion of patients who achieved CR, PR, or stable disease.

In general, categorical data will be summarized as counts and percentages (or proportions) and continuous data will be summarized with descriptive statistics such as mean, standard deviation, median, minimum and maximum.

Final analyses will be carried out after the last participant has completed their last trial visit, the trial database has been authorized by Dynavax as complete and final, and major protocol deviations have been identified. Patient data will be reviewed for major protocol deviations by the Medical Monitor prior to database lock. A listing of patients with major protocol deviations will be provided, sorted by treatment and describing their deviations. Efficacy and safety data from each cohort may be analyzed and reported separately from other cohorts. In addition, safety data will be summarized overall and for each separate tumor indication.

12.2 Sample Size Considerations

The Phase 1 trial is designed to allow preliminary assessments of safety, biological activity, and biomarkers in approximately 24 patients. Phase 2 of this trial is designed to allow preliminary assessments of efficacy, safety, and changes in biomarkers in approximately 210 patients. All analyses will be descriptive.

The Phase 1 trial sample size is based on a modified 3 + 3 dose-escalation trial design.

For the Phase 2 expansion cohorts, the sample sizes were determined based on power analysis of hypothesis tests and/or confidence intervals, although the efficacy analyses will be descriptive.

In Expansion Cohort 1, approximately 60 anti PD 1/L1 naïve patients with metastatic melanoma will be enrolled. The null hypothesis that the response rate is < 35% will be tested against a 1-sided alternative at a significance level of 0.05. The design will provide greater than 90% power if the true response rate is > 55%. There will be no adjustments for multiplicity.

An exploratory sub-group analysis will be performed for those Expansion Cohort 1 subjects with PD-L1 negative tumors (ie, < 1% positivity) at baseline. It was estimated that this subgroup will have approximately 30 subjects. The analysis will have 80% power to reject the null hypothesis that the response rate is <15% with a one-sided test at a significance level of 0.05 when the true response rate is 35%. There will be no adjustments for multiplicity.

In Expansion Cohort 2, approximately 25 metastatic melanoma patients who have disease progression on anti-PD-1/L1 therapy will be enrolled. The null hypothesis that the true response rate is 10% will be tested against a 1-sided alternative and will be rejected if 6 or more responses are observed. This design yields a type I error rate of 0.05 and 80% power when the true response rate is 30%. There will be no adjustments for multiplicity.

In Expansion Cohort 5, approximately 25 anti-PD-1/L1 naïve melanoma patients will be enrolled. This will allow preliminary estimate of the response rate associated with the dose and dosing schedule chosen for Expansion Cohort 5. If 14 or more responses are observed, the 95% exact confidence interval will yield a lower bound of no less than 37%.

In Expansion Cohort 3, approximately 25 anti-PD-1/L1 naïve HNSCC patients will be enrolled. The null hypothesis that the response rate is $< 20\%$ will be tested against a 1-sided alternative at a significance level of 0.05. The design will provide greater than 80% power if the true response rate is $> 40\%$. There will be no adjustments for multiplicity.

In Expansion Cohort 4, approximately 25 HNSCC patients who have disease progression on anti-PD-1/L1 therapy will be enrolled. The null hypothesis that the true response rate is 5% will be tested against a 1-sided alternative and will be rejected if 4 or more responses are observed. This design yields a type I error rate of 0.05 and 80% power when the true response rate is 21%. There will be no adjustments for multiplicity.

In Expansion Cohort 6, approximately 25 anti-PD-1/L1 naïve HNSCC patients will be enrolled. This will allow preliminary estimate of the response rate associated with the dose and dosing schedule chosen for Expansion Cohort 6. If 9 or more responses are observed, the 95% exact confidence interval will yield a lower bound of no less than 20%.

In Expansion Cohort 7, approximately 25 patients who are refractory or resistant to anti-PD-1/L1 therapy will be enrolled. This will allow preliminary estimate of the response rate associated with the dose and dosing schedule chosen for Expansion Cohort 7. If 4 or more responses are observed, the 95% exact confidence interval will yield a lower bound of no less than 5%.

In Expansion Cohort 8, approximately 50 metastatic melanoma patients who are refractory or resistant to anti-PD-1/L1 therapy will be enrolled. If 13 or more responses are observed, the 95% exact confidence interval will yield a lower bound of no less than 15.0%.

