In Expansion Cohort 8, approximately 50 metastatic melanoma patients who are refractory or resistant to anti-PD-1/L1 therapy will be enrolled. If 13 or more responses are observed, the 95% exact confidence interval will yield a lower bound of no less than 15.0%.

In Expansion Cohort 3, approximately 25 anti-PD-1/L1 naïve HNSCC patients will be enrolled. The null hypothesis that the response rate is < 20% will be tested against a 1-sided

alternative at a significance level of 0.05. The design will provide greater than 80% power if the true response rate is $> 40\%$. There will be no adjustments for multiplicity.

In Expansion Cohort 6, approximately 25 anti-PD-1/L1 naïve HNSCC patients will be enrolled. This will allow a preliminary estimate of the response rate associated with the dose and dosing schedule chosen for Expansion Cohort 6. If 9 or more responses are observed, the 95% exact confidence interval will yield a lower bound of no less than 20%.

In Expansion Cohort 4, approximately 25 HNSCC patients who have disease progression on anti-PD-1/L1 therapy will be enrolled. The null hypothesis that the true response rate is 5% will be tested against a 1-sided alternative and will be rejected if 4 or more responses are observed. This design yields a type I error rate of 0.05 and 80% power when the true response rate is 21%. There will be no adjustments for multiplicity.

In Expansion Cohort 7, approximately 25 HNSCC patients who are refractory or resistant to anti-PD-1/L1 therapy will be enrolled. This will allow a preliminary estimate of the response rate associated with the dose and dosing schedule chosen for Expansion Cohort 7. If 4 or more responses are observed, the 95% exact confidence interval will yield a lower bound of no less than 5%.

Although changes to the groupings for the final analysis will be made, there is no impact to the sample size calculation, as all analyses will be descriptive. At some places in above sample size calculation one-sided significance level of 0.05 was referenced, to standardize the analyses, two-sided significance level of 0.05 is used throughout. Power and 95% exact confidence interval descriptions are still applicable if the underlying conditions in various analysis groups hold.

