9.6.1 Objective Response Rate

The ORR is the proportion of patients who achieve a response of either CR or PR. ORR will be summarized and 95% Clopper Pearson confidence interval will be reported for each dose or analysis group.

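### SAP Section 5.0 moves to two-sided 0.05 but keeps the 80% power stated one-sided for the PD-L1-negative subgroup; under the SAP's own interval, power at 30 patients is about 64%

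*Protocol*

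**What the plan says.** Protocol Section 12.2 plans an exploratory analysis of Cohort 1 patients whose tumours are PD-L1 negative at baseline. On its size it says: "It was estimated that this subgroup will have approximately 30 subjects". On its power it says: "The analysis will have 80% power to reject the null hypothesis". The null is a response rate below 15%, the true rate is 35%, and the test is one-sided at 0.05. The synopsis and SAP Section 5.0 carry the same statement. None of these places names a test or a cutoff for this subgroup, whereas Cohorts 2 and 4 do have a minimum number of responses.

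SAP Section 5.0 then changes the level at its end: "two-sided significance level of 0.05 is used throughout". It adds: "Power and 95% exact confidence interval descriptions are still applicable if the underlying conditions in various analysis groups hold". For the objective response rate, SAP Section 9.6.1 says that a "95% Clopper Pearson confidence interval will be reported for each dose or analysis group".

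Protocol Section 12.1 says: "No pre-specified hypothesis testing will be performed". SAP Section 9.0 says the same.

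**The concern.** Going from one-sided to two-sided 0.05 cuts the error allowed in the upper tail from 0.05 to 0.025 under an equal-tailed rule. More responses are then needed to exclude 15%, so power against 35% falls. The SAP's proviso concerns conditions in the regrouped analysis sets, such as their size and response rates. It does not cover a change of sidedness.

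What is at stake is interpretation. Suppose a reader sees a subgroup interval that includes 15% and relies on the printed 80%. That reader would put the chance of missing a true 35% rate at 20%. Under the SAP's own interval with 30 patients, it is 100% − 64.2% = 35.8%.

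**Working it through.** **Inputs.** From Protocol Section 12.2 and SAP Section 5.0: n about 30, p0 = 0.15, p1 = 0.35, one-sided 0.05, stated power 80%. From the end of SAP Section 5.0: two-sided 0.05. I take this as 0.025 in the upper tail, which is an assumption but matches the equal-tailed Clopper-Pearson interval of SAP Section 9.6.1. The test method is not given, so several are shown.

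**Step 1: the stated 80%, one-sided 0.05, n = 30.**

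Normal approximation: power = Φ[(p1 − p0 − c − z·s0)/s1], with
- s0 = √(0.15 × 0.85/30) = 0.0652
- s1 = √(0.35 × 0.65/30) = 0.0871
- z = 1.645
- c = 1/(2 × 30) = 0.0167 with continuity correction, 0 without

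Results:
- With correction: Φ[(0.20 − 0.0167 − 0.1072)/0.0871] = Φ(0.874) = 80.9%. This reproduces the plan's figure.
- Without correction: Φ[(0.20 − 0.1072)/0.0871] = Φ(1.065) = 85.7%.

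Exact binomial: take the smallest r with P(X ≥ r | n, 0.15) ≤ 0.05; power is P(X ≥ r | n, 0.35).
- n = 30: r = 9, size 0.028, power 77.5%. (r = 8 would give 87.6% power but size 0.070.)
- n = 28: r = 8, power 81.8%.
- n = 29: r = 9, power 73.5%.
- n = 31: r = 9, power 81.1%.

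**Step 2: the SAP's rule with its own interval, n = 30.** The 95% Clopper-Pearson lower bound is 14.7% at 9/30, which does not exclude 15%, and 17.3% at 10/30, which does. Equivalently, P(X ≥ 9 | 30, 0.15) = 0.0278 exceeds 0.025, while P(X ≥ 10 | 30, 0.15) = 0.0097 does not. Power is P(X ≥ 10 | 30, 0.35) = 0.64246, or 64.2%. That is 80 − 64.2 = 15.8 points below the stated figure.

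**Step 3: allow for the size being approximate.** Exact power with 0.025 in the upper tail:

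| n | cutoff | power at 35% |
|---|---|---|
| 28 | 9 | 69.1% |
| 29 | 9 | 73.5% |
| 30 | 10 | 64.2% |
| 31 | 10 | 68.9% |
| 32 | 10 | 73.2% |
| 33 | 10 | 77.0% |
| 34 | 10 | 80.4% |

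No size from 26 to 33 reaches 80%. At n = 35 the cutoff rises to 11 and power drops back to 72.8%.

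**Step 4: other methods under two-sided 0.05, n = 30.** With z = 1.960:
- Normal with correction: Φ[(0.20 − 0.0167 − 0.1278)/0.0871] = Φ(0.638) = 73.8%.
- Normal without correction: Φ[(0.20 − 0.1278)/0.0871] = Φ(0.829) = 79.7%.
- Exact test with the minimum-likelihood two-sided p-value: 9/30 gives p = 0.035, so the cutoff stays at 9 and power is 77.5%.

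**Step 5: one-sided against two-sided, n = 30.**

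| method | one-sided 0.05 | two-sided 0.05 |
|---|---|---|
| exact, equal-tailed | 77.5% | 64.2% |
| exact, minimum-likelihood | 77.5% | 77.5% |
| normal, corrected | 80.9% | 73.8% |
| normal, uncorrected | 85.7% | 79.7% |

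None of these methods gives 80% under both rules. The one that reproduces the protocol's figure loses about 7 points under the SAP's.

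**The case against.** A reader might infer from the exact 77.5% at n = 30 that the protocol's one-sided 80% is itself an arithmetic error. The documents do not support that. No test is named for this subgroup, and the size is an estimate. The corrected normal approximation gives 80.9%, and exact power exceeds 80% at 28 and 31 patients. Exact calculation does reproduce the 80% for Cohorts 2 and 4 (80.7% and 80.1% with their stated cutoffs). That makes it a reasonable benchmark here, but not a stated method. The gap at n = 30 is an effect of method and discreteness.

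The best defence of the SAP is the uncorrected normal approximation. It gives 79.7% two-sided at 30 patients and needs n = 30.3 for 80%. On that method the carried-over figure is nearly right, but the one-sided power would then be 85.7%, not the 80% printed. The approximation also does not match the exact interval that the SAP reports.

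The 64.2% falls at a low point of the exact power curve, so it should not be quoted without its range. That stands, and the range is given above. It also stands that little depends on the figure:
- Both documents call the analyses descriptive and plan no hypothesis test.
- SAP Section 6.3 makes PD-L1 subpopulations optional, and this subgroup is not among the analysis groups in SAP Sections 2.0 and 9.11.
- Protocol Section 12.0 says that exploratory objectives are not pursued as of Amendment 9.

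Finally, the carry-over sentence covers every one-sided power statement in SAP Section 5.0. The calculation here is for the subgroup only.

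**Conclusion.** The SAP's statement that power still applies is not supported for the PD-L1-negative subgroup. With the equal-tailed exact rule that matches its Clopper-Pearson interval, power is 64.2% at 30 patients. That is 15.8 points below the printed figure, and 3.0 to 15.8 points below it for 28 to 33 patients. This rests on reading two-sided 0.05 as equal-tailed. Other methods put the figure at 73.8% to 79.7% at n = 30.

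Two stronger readings should be avoided. The protocol's one-sided 80% is not shown to be wrong. No trial decision is shown to turn on this figure, since the analysis is exploratory, optional and untested. Severity is low: a printed claim is inconsistent with the rule printed beside it.

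**What to change.** In SAP Section 5.0, delete the statement that power remains applicable after the move to two-sided 0.05, at least for this subgroup. Then do one of the following:

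- Keep the one-sided 0.05 level for the subgroup and name the method. For the exact test at n = 30: cutoff 9, size 0.028, power 78%.
- Keep two-sided 0.05 and restate power as about 64% at n = 30 (cutoff 10), with a range of 64% to 77% for 28 to 33 patients.

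Give either set as illustrative figures for a descriptive exploratory analysis, not as a rejection rule. The subgroup size is not controlled and the cutoff moves with it: the one-sided exact cutoff is 8 at n = 28 and 10 at n = 34.

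The cost is a change of text. It needs no added patients and no change to the reported intervals.

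### The 95% exact lower bounds given for Cohorts 5 to 8 are one-sided; the SAP's two-sided 95% Clopper-Pearson interval falls short of all four

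*Protocol*

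**What the plan says.** Protocol 12.2 gives each of these cohorts a sample size, a response count and a guaranteed lower bound:

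- Cohort 5: "In Expansion Cohort 5, approximately 25 anti-PD-1/L1 naïve melanoma patients will be enrolled", and "If 14 or more responses are observed, the 95% exact confidence interval will yield a lower bound of no less than 37"%.
- Cohort 6, about 25 patients: "If 9 or more responses are observed, the 95% exact confidence interval will yield a lower bound of no less than 20"%.
- Cohort 7, about 25 patients: "If 4 or more responses are observed, the 95% exact confidence interval will yield a lower bound of no less than 5"%.
- Cohort 8, about 50 patients: "If 13 or more responses are observed, the 95% exact confidence interval will yield a lower bound of no less than 15.0"%.

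The same statements appear in the Synopsis (Statistical Methods) and in SAP 5.0. None of them says whether the bound is one-sided or two-sided. The tests described for Cohorts 1 to 4 in the same section are explicitly 1-sided.

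The closing paragraph of SAP 5.0 acknowledges the one-sided level used in places and says that "to standardize the analyses, two-sided significance level of 0.05 is used throughout". It then adds: "Power and 95% exact confidence interval descriptions are still applicable if the underlying conditions in various analysis groups hold". For reporting, SAP 9.6.1 says: "ORR will be summarized and 95% Clopper Pearson confidence interval will be reported for each dose or analysis group".

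**The concern.** A 95% Clopper-Pearson interval, as normally reported, puts 2.5% in each tail. The printed lower bounds look too high for that, and they all look as if 5% had been put in the lower tail. In the Protocol alone this would only be unstated sidedness. The SAP turns it into a contradiction by moving to a two-sided level and, in the next sentence, reaffirming the interval statements.

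These bounds are the only quantitative justification given for the sizes of Cohorts 5 to 8. If they are wrong on the stated basis, the plan claims better precision than its own interval delivers. A reader who computes the SAP interval at a planned count and size will not find the promised bound.

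**Working it through.** **Inputs.** Responses x, planned size n and printed bound L, from Protocol 12.2: Cohort 5 (14, 25, 37%), Cohort 6 (9, 25, 20%), Cohort 7 (4, 25, 5%), Cohort 8 (13, 50, 15.0%). Method from SAP 9.6.1: Clopper-Pearson. Level from SAP 5.0: two-sided 0.05, i.e. 0.025 per tail.

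**Formula.** The exact lower limit with lower-tail probability a is the a-quantile of a Beta(x, n − x + 1) distribution. A one-sided 95% bound uses a = 0.05 and is the same as the lower limit of a two-sided 90% interval. A two-sided 95% interval uses a = 0.025.

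**Step 1: reproduce the printed figures (a = 0.05).**

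| Cohort | x/n | Printed bound | One-sided 95% | One response fewer, one-sided |
|---|---|---|---|---|
| 5 | 14/25 | 37% | 37.86% | 13/25: 34.14% |
| 6 | 9/25 | 20% | 20.24% | 8/25: 17.03% |
| 7 | 4/25 | 5% | 5.66% | 3/25: 3.35% |
| 8 | 13/50 | 15.0% | 16.12% | 12/50: 14.47% |

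All four bounds hold one-sided, and each printed count is the smallest that works. The same pattern in four cohorts suggests a 1-sided 0.05 calculation, although the text does not say so.

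**Step 2: apply the SAP's two-sided 95% interval (a = 0.025).**

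| Cohort | x/n | Two-sided 95% interval | Printed bound | Shortfall in points |
|---|---|---|---|---|
| 5 | 14/25 | 34.93% to 75.6% | 37% | 2.1 |
| 6 | 9/25 | 17.97% to 57.5% | 20% | 2.0 |
| 7 | 4/25 | 4.54% to 36.1% | 5% | 0.5 |
| 8 | 13/50 | 14.63% to 40.3% | 15.0% | 0.4 |

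None is met. Reaching the printed bounds two-sided takes one more response in every cohort: 15/25 (38.7%), 10/25 (21.1%), 5/25 (6.8%) and 14/50 (16.2%).

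**Step 3: cross-check with binomial tails.** P(X ≥ x) when the true rate equals the printed bound is 0.0412, 0.0468, 0.0341 and 0.0301 for Cohorts 5 to 8. Each lies between 0.025 and 0.05, so each bound is excluded at one-sided 0.05 but not at 0.025 per tail. The two-sided confidence level at which the printed bound just holds is 1 − 2 × tail: 91.8%, 90.6%, 93.2% and 94.0%.

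**Step 4: dependence on n.** With the counts fixed, the two-sided limits reach the printed bounds only with fewer patients: n ≤ 23 in Cohort 5 (38.5% at 23), n ≤ 22 in Cohorts 6 and 7 (20.7% and 5.2% at 22) and n ≤ 48 in Cohort 8 (15.3% at 48). In the other direction, at n = 26 even the one-sided bounds for Cohorts 5 and 6 fail (36.2% and 19.4%).

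**The case against.** The strongest reply is that the Protocol contains no arithmetic error. It does not name Clopper-Pearson, the neighbouring cohorts use 1-sided tests, and every printed bound is true one-sided. That is fair. What goes wrong is the missing label, combined with the SAP's two-sided level and its statement that the descriptions carry over. The SAP sentence is conditional, but the condition does not rescue it: the bounds fail even when the planned size and count occur exactly.

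A second reply is that other two-sided 95% intervals exist. The Blaker exact interval would meet the bounds for Cohorts 7 and 8 (5.7% and 15.5%) but not for Cohorts 5 and 6 (35.5% and 19.0%). The Wilson interval would meet all four (37.1%, 20.2%, 6.4%, 15.9%), but it is not exact. The SAP names neither.

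Rounding to a whole percent would bring Cohorts 7 and 8 up to the printed values, but the text promises no less than the bound and prints 15.0% to one decimal. Rounding does not help Cohorts 5 or 6. The approximate sample sizes help only if two or three fewer patients are enrolled and the response count is unchanged.

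The point about consequence stands. Enrolment is closed, Amendment 9 ends efficacy data collection, and no hypothesis test or decision depends on these counts. SAP 2.0 also pools these cohorts with others for reporting, so an interval for exactly 14/25 or 13/50 is not a planned result. The reported intervals will be computed from the data and are unaffected by section 5.0.

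**Conclusion.** The concern holds. On the interval the SAP specifies, all four printed lower bounds are overstated at the planned sizes: by about 2 points in Cohorts 5 and 6, and by about half a point or less in Cohorts 7 and 8. They are correct only if read as one-sided 95% Clopper-Pearson bounds, so the SAP 5.0 statement that they still apply under a two-sided 0.05 level is wrong.

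This rests on n = 25 and n = 50 exactly, on Clopper-Pearson as named in SAP 9.6.1, and on reading its 95% interval as two-sided, in line with SAP 5.0. It is a minor correction to stated precision. It changes no reported estimate and no decision.

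**What to change.** Make one of two wording changes in the Synopsis, Protocol 12.2 and SAP 5.0, or record it as a correction in the clinical study report:

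- Restate the bounds as two-sided 95% Clopper-Pearson limits: 34.9%, 18.0%, 4.5% and 14.6%. If the no-less-than phrasing is kept, write 17.9% for Cohort 6, because the limit is 17.97%.
- Or keep 37%, 20%, 5% and 15.0% and label them as one-sided 95% (equivalently two-sided 90%) exact bounds for n = 25 (Cohorts 5 to 7) and n = 50 (Cohort 8).

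In either case, amend the closing paragraph of SAP 5.0 so that it no longer says the interval descriptions carry over unchanged to a two-sided 0.05 level. The response counts can stay as they are.

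The cost is wording only, with no change to enrolment or analyses. With enrolment closed, a note in the study report is enough; Protocol 12.0 already sends changes in statistical methods there. The first option makes the stated precision slightly less favourable.
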